Treatment under investigation	
All drugs whose properties are being tested in the study, as well as their associated control treatments.
 
This includes any placebo, any active control, and also approved drugs used outside their approved indications/doses or tested in a fixed combination.
 
The investigational treatment generally does not include concomitant background therapies specified by the protocol when these are standard treatments for that indication

Drug number	A unique identifier on the label of each package of the study/investigational drug in studies dispensing the drug using an IRT system
Protocol	A written record of all procedures to be followed in a study that describes all administrative, documentation, analytical, and clinical processes to be used in the study.
Arm	A single component of a study that contains different objectives or populations within a single study. Common parts of a study include: a single-dose part and a multiple-dose part, or a part involving participants with established disease and those with newly diagnosed disease.

Period	A subdivision of a crossover study
Premature withdrawal of a participant/patient	The point at which a participant leaves the study before the planned completion of all study treatment administrations and/or assessments; at this point, all study treatment administrations are discontinued and no further assessments are planned, unless the participant is followed up regarding disease progression and/or survival
Randomization number	A unique identifier assigned to each randomized participant, corresponding to a specific treatment arm assignment
Study drug/treatment	Any single drug or combination of drugs administered to the patient as part of the required study procedures; includes the investigational drug, active treatment periods (run-in), or background therapy
Discontinuation of study/investigational treatment	The point/time at which the participant permanently discontinues use of the study/investigational treatment for any reason; may or may not also be the point/time of the patient's early withdrawal
Participant number	A number assigned to each patient included in the study
Variable	A measured value or an assessed response that is determined at a specific assessment and used in data analysis to evaluate the investigational drug in the study

PROTOCOL OVERVIEW

Protocol - Long COVID Chronic Fatigue

Title:	“A multicenter, adaptive, randomized, double-blind, placebo-controlled, prospective study of pharmacological interventions in participants with a clinical presentation consistent with Long COVID-19: The REVIVE-TOGETHER Protocol”
Abbreviated Title:	Long COVID Chronic Fatigue Syndrome
Investigational product:	Metformin, Fluvoxamine
Indication:	Long COVID with chronic fatigue syndrome
Phase:	PHASE III – New indication
Sponsor:	CARDRESEARCH - Cardiology Care and Research, LLC
Study code	LONG-COVID_REVIVE_TOGETHER
Principal Investigators:	[name], [name], [name], [name], [name]
Proposing institution:	Cardresearch - Cardiology Care and Research, LLC
Collaborating Researchers Scientists	[name], PhD. [name] [name]
Objectives:	
The primary objective is to compare metformin, fluvoxamine, and placebo for the mean Fatigue Severity Scale (FSS) score at 60 days after randomization. The secondary objectives are:
 
 1. To compare metformin, fluvoxamine, and placebo for the mean FFS score 30 days after randomization. 2. To compare metformin, fluvoxamine, and placebo for the mean FSS score 90 days after randomization. 3. To compare metformin, fluvoxamine, and placebo regarding the mean difference in change in health-related quality of life (EQ-5D-5L) at 60 days after randomization. 4. Compare metformin, fluvoxamine, and placebo for the odds ratio of all-cause mortality at 60 days after randomization. 5. Compare metformin, fluvoxamine, and placebo for the odds ratio of unexpected hospitalization from all causes at 60 days. 6. To assess the safety of metformin and fluvoxamine in this population of participants. 7. To assess the medium-term effects (90 and 180 days) of the investigational medical products on the chronic fatigue scale (FSS scale) and quality of life (EQ-5D-5L).
Design:	A multicenter, double-blind, adaptive, prospective, randomized, parallel-group, placebo-controlled study evaluating metformin and fluvoxamine with a 90-day follow-up after randomization.
Inclusion Criteria	Participants must meet all of the following criteria to be eligible for participation in this study:

	
 1. Age 18 years or older at the time of screening. 2. Willing and able to provide written informed consent, or have a legal representative who can provide informed consent (when approved locally and nationally). 3. A previous SARS-CoV-2 infection confirmed by the participant (e.g., reports having had a positive nucleic acid amplification test or a positive professional-use or self-test SARS-CoV-2 rapid antigen test). 4. Participants with a clinical presentation consistent with LONG COVID according to international definitions: (www.nice.org.uk/guidance/ng188 , https://www.who.int/publications/i/item/WHO-2019-nCoV-Post_COVID-19_condition-Clinical_case_definition-2021.1), and fatigue symptoms with an average score of at least 03 on the Fatigue Scale (FSS); 5. Have had the most recent episode of COVID-19 within 24 months of screening; 6. Not currently hospitalized or in need of hospitalization, or having been hospitalized in an intensive care unit during the COVID-19 episode. 7. Participants with the following vital signs: 
 a. Heart rate between 55 and 100 bpm; b. Temperature below 38°C; c. Oxygen saturation \geq 95%. 8. Participants who are capable of becoming pregnant or whose partners are capable of becoming pregnant must agree to use appropriate contraceptive methods during the study and for up to 90 days of follow-up. 9. Symptoms of fatigue cannot be attributed to another cause (in the researcher's opinion). 10. Willingness to follow all study procedures.
Exclusion criteria	
Participants who meet any of the following criteria will not be eligible to participate in the study:
 
 1. Known acute SARS-CoV-2 infection; 2. Inability to understand the content of the Informed Consent Form or to follow the study procedures; 3. Known prior diagnosis of myalgic encephalomyelitis/chronic fatigue syndrome, unrelated to SARS-CoV-2 infection; 4. Known pre-existing dysautonomia, unrelated to SARS-CoV-2 infection; 5. Diabetes mellitus (exclusion criterion for the Metformin and Metformin Placebo arms); 6. Known history of creatinine clearance below 30 mL/min or on dialysis. 7. Known stroke within the 3 months prior to screening; 8. Known severe anemia, defined as < 8 g/dL; 9. Body Mass Index (BMI) > 40. 10. Known diagnosis of Lyme disease; 11. Any use of illicit drugs other than marijuana within 30 days prior to informed consent;

	
 12. Pregnant women or women of childbearing age who do not agree to use an effective method of contraception for 90 days from the date of signing this consent form; 13. Women who are breastfeeding; 14. Expected hospitalization for elective surgical procedures lasting more than 48 hours; 15. Contraindications for the METFORMIN arm 
 a. Participants currently taking metformin; b. Participants with creatinine clearance < 30 ml/min, a history of KIDIGO IV, or currently undergoing dialysis. 16. Contraindications for the FLUVOXAMINE arm 
 a. Use of serotonin reuptake inhibitors (donepezil, fluoxetine, escitalopram, paroxetine); 17. Current severe comorbid psychiatric disorder (e.g., clinical depression, anxiety, sleep disorder, eating disorder, substance abuse) that is uncontrolled and associated with significant symptoms or requiring the use of a medication contraindicated in this study; 18. Clinical history of moderate to severe hepatic impairment or hepatic cirrhosis with a Child-Pugh score of C or higher; 19. Clinical history of severe chronic lung disease with significant limitation of activities; 20. Inability of the participant to provide informed consent or adhere to the procedures proposed in the study; 21. Taking medications known to cause chronic fatigue as a side effect (except for participants with chronic cardiovascular disease who are on chronic beta-blocker therapy); 22. Known hypersensitivity and/or intolerance to fluvoxamine or metformin; 23. Any clinical condition that, in the investigator's opinion, may preclude participation in this study.
Primary and secondary outcomes:	
The primary outcome is a reduction in the FSS score of at least one standard deviation 60 days after randomization.
 
The secondary outcomes are:
 
 1. The FFS score 30 days after randomization. 2. The FFS score 90 days after randomization. 3. HRQL, assessed using the EuroQol-5D-5L 60 days after randomization. 4. All-cause mortality up to 60 days after randomization. 5. Unexpected hospitalization from any cause up to 60 days after randomization. 6. Safety and tolerability of the investigational products 7. Adverse events experienced by participants during treatment
Procedures	Screening procedures

Before any study-specific procedure, the participant will receive an explanation of all study procedures and must date and sign an informed consent form (ICF) approved by a Research Ethics Committee (REC). The screening visit will be conducted in person. The ICF may be provided in physical, paper form or via an electronic informed consent form, in accordance with the guidelines recommended by CONEP.

Eligible participants will be identified during the clinical consultation. Participants identified as having a probable diagnosis of Long COVID will be invited to learn about the research project. If they express interest, they will be referred to a designated and trained research team member who will present the proposed research program, verify the criteria for diagnosing Long COVID, and, if the diagnosis is confirmed, present the Informed Consent Form (ICF), which will be provided in accordance with current regulatory standards for clinical research. Research procedures will only begin if participants who express interest in participating in the research program sign the TCLE, which is the first step in the research process. During the screening visit, participants will receive a unique participant number, which will be generated during the registration of the screening visit in the IWRS.

Female participants are initially screened to identify those who meet the eligibility criteria. After obtaining informed consent, participants of childbearing potential will be asked to take a pregnancy test. Participants will also be asked to complete the FSS to determine if they have a moderate score to qualify for participation.

Screening Visit Procedures and Randomization

The screening visit and randomization procedures should be performed immediately after confirming eligibility criteria and obtaining consent to participate in the study and may be performed during the same visit. The following procedures will be performed:

1. Obtaining the TCLE;
2. EQ-5D-5L questionnaire;
3. FSS Scale (chronic fatigue)
4. Verification of inclusion/exclusion criteria;
5. Urinary pregnancy test for females of childbearing age;
6. Registration in the IWRS;
7. Demographic data;
8. Medical history;
9. Comorbidities and risk factors;
10. Concomitant medications;
11. Physical examination findings;
12. Vital signs (including temperature, heart rate, respiratory rate, and oxygen saturation in room air);
13. Details of your COVID-19 medical history;
14. Randomization and administration of the first dose of the investigational product/placebo.

-
15. Delivery of the investigational product/placebo and instructions regarding it.
 16. Instructions regarding subsequent visits.

Investigational product

Participants will receive the investigational products and instructions on dosing, which must be taken as directed for a period of 60 days.

Follow-up procedures

Follow-up visits will take place on days 7, 30, 60, 90, and 180 (± 7 days) after randomization. The visits on days 7, 30, 90, and 180 should preferably be conducted via telephone, telemedicine, or social media. The visit on day 60 should preferably be conducted at the research center, but may also be conducted via telephone, telemedicine, or social media. Participants will be asked to complete the FSS and the EQ-5D-5L 30 days, 60 days, and 90 days after randomization. In addition, on days 30, 60, and 90, the local research team will verify the participant's status and clinical outcomes (all-cause mortality and unplanned hospitalization). The research team will collect data on adherence to the experimental product and the placebo. The research team will also document concomitant medications. Participants will be monitored for adverse events and laboratory abnormalities at each visit.

The above data will be collected directly from the participant, the participant's medical record, or the healthcare professional(s) responsible for the participant's care. If a participant is unable to return to the healthcare center for a follow-up visit, the research team may contact the participant and conduct the visit by telephone. Data may also be collected via valid methods of electronic communication.

Study Committee

The event adjudication committee is responsible for ensuring that the source documents supporting the study event/outcome are adequate and that the diagnosis of adverse events is correct and supported by supporting documentation. In the absence of such documentation, events will be reviewed in accordance with good research practices, and the information certified by the principal investigator at each center will be attached to the study file.

	
The independent Data Monitoring Committee (DMC) has a predefined plan for statistical data analysis and research safety that was approved prior to the start of this clinical trial. The analyses follow good clinical practices, being conducted in a blinded manner with possible unblinding regarding the indicated study arms if the pre-specified criteria for such unblinding are met (see the committee's composition in the document attached to the regulatory file).
 
The steering committee has been in place since the start of the clinical trial, and its purpose is to ensure the scientific integrity of the study, as well as to oversee operational aspects for the proper conduct of the research.

Sample Size	
The sample size is 1,500 participants, with 500 participants per treatment arm under evaluation, including the placebo arm, and its operational characteristics were confirmed through closed-form, analytical calculations, and numerical methods. The operational characteristics for the head-to-head comparison of the treatment arm versus the placebo arm in reducing the mean fatigue score measured by the Fatigue Severity Scale (1 to 9) on day 60 are determined. For each head-to-head comparison against the placebo arm, the Type I error rate (alpha) is set at 0.025 (one-sided) using a Bayesian normal-normal model. For the planning of our study, we assumed a plausible standard deviation of 1.7, which was estimated from a recent study that evaluated the psychometric properties of the Fatigue Severity Scale in participants recovering from COVID-19¹.
 
With the proposed sample size of 1,500 participants (3 arms containing 500 participants each), the study will have adequate statistical power to detect a clinically important treatment effect. A difference of 0.45 has been suggested as a minimally important difference (MID) on the Fatigue Severity Scale in population groups of participants with multiple sclerosis and chronic fatigue². Even with a 10% dropout rate, our estimated power to detect a difference of 0.45 is above 90%.
 
Interim analyses are planned upon reaching 25%, 50%, and 75% of the study population. The unblinded statistician advising the DMC will make recommendations based on the continuous evaluation of overall data and epidemiological data on Long COVID from Brazil and the state of Minas Gerais. We are continuously monitoring the literature for new findings relevant to chronic fatigue and to participants with Long COVID, and this protocol will be updated as needed based on relevant information and submitted to regulatory authorities for ethical review.

Statistical Methods	
Overview
 
Study design
 
A phase III adaptive, randomized clinical trial to evaluate the efficacy and safety of new treatments and existing medications (new therapeutic

indications) in participants with symptoms of chronic fatigue from Long COVID-19 following resolution of acute COVID-19 infection.

Internal pilot phase

Phase to assess the feasibility of the study and address any issues that may arise, aiming to refine the trial, with a focus on identifying unforeseen feasibility problems and resolving them to improve the overall success of the research. In particular, we will evaluate issues related to recruitment, informed consent, availability and administration of medications, data collection and recording, and the safety and tolerability of the proposed interventions. There will be no analysis of clinical results at the end of this phase—since participants will be transferred to the main study and analyzed collectively. This will involve a blinded analysis of up to 10% of the target sample size, with an initial focus on the safety and tolerability of the IPs under evaluation.

The main clinical study

Full implementation of the clinical trial, with the primary clinical endpoint being a reduction in perceived fatigue on the Fatigue Severity Scale (FSS). This phase is an adaptive phase, with three interim analyses to evaluate therapeutic effects using the placebo arm as the baseline. The main adaptations include:

- i) Discard the placebo arm if there is strong evidence of benefit.
- ii) Discard active study arms that show statistically unfavorable results.
- iii) Partnering with study arms of common interest from other study platforms, with the goal of obtaining responses in less time compared to conducting the study in isolation.

Randomization

Participants will be randomly assigned to one of the study arms in an equal allocation (e.g., 1:1:1). Stratified permuted-block randomization will be used for this study. Randomization will be stratified by participating primary care facility with varying block sizes of participants.

The analysis and reporting of results follow the CONSORT guidelines (www.consort-statement.org). The participant selection process and study flow will be summarized using a flow diagram. The results of the analysis of participants' demographic data and baseline outcome variables (primary and secondary) will be summarized using descriptive summary measures: expressed as mean (standard deviation) or median (minimum–maximum) for continuous variables, as appropriate, and number (percentage) for categorical variables. We will adopt an intention-to-treat principle to analyze all results.

Bayesian statistics is the standard statistical framework for this study. Statistical analyses of IPs are limited to concomitantly randomized controlled data. Sequential designs with Bayesian stopping rules are expected to be used to evaluate multiple IPs. Recruitment for an IP will be stopped before the maximum sample size using decision rules pre-specified in the statistical analysis plan (SAP). The maximum sample size and corresponding decision rules are determined a priori by dedicated statisticians and methodologists, who will remain blinded during the conduct of the study. The statistical analysis plan (SAP) was formulated to ensure that the expected one-sided Type I error is less than 0.025 for each treatment. We will also use multiple imputation to handle missing data. For all models, results will be expressed as the effect reported as the mean difference for continuous outcomes, odds ratios (OR) for binary outcomes, and hazard ratios (HR) for time-to-event outcomes, with their respective 95% confidence or credibility intervals.

All analyses will be performed using the latest version of R at the time of analysis. A detailed analysis plan will be developed prior to database lock. Any relevant safety data specific to Brazil will be immediately reported to our group for appropriate regulatory action.

The 90- and 180-day visits are post-study follow-up visits. The primary and secondary outcomes of the study are planned to be based on the D60 visit after randomization.

Analysis of Primary and Secondary Outcomes

To analyze the primary outcome of the mean fatigue score at day 60 measured by the Fatigue Severity Scale, we will use the Bayesian normal-normal model with non-informative prior distributions for the group means. This analysis will be adjusted for prespecified covariates. For all other continuous outcomes, we will use similar modeling approaches. For all binary outcomes, we will use logistic regression for analysis. The Cox proportional hazards model will be used for all time-to-event outcomes. All analyses of secondary outcomes will be exploratory in nature, without adjustment for alpha for multiple secondary analyses.

Sensitivity Analyses

We will perform several sensitivity analyses to assess the robustness of the results, particularly for the primary outcome. These include:

1. Protocol analysis based only on participants who adhered to the protocol as described;
2. concurrent risk analysis: this analysis will adjust for death as a competitive risk for any outcome;
3. Missing data analysis: This analysis will assess the impact of missing data on the primary outcomes.
4. We will also conduct sensitivity analyses to account for any unforeseen issues that arise during the study process and that may affect the main conclusions.

Subgroup analyses

We will conduct several subgroup analyses to assess the consistency of effects across subgroups of participants:

1. Age—assumption that younger participants will benefit more than older ones.
 2. Gender—assumption that women will benefit more than men.
 3. Vaccination status—assumption that vaccinated individuals will benefit more than those who did not receive the vaccine.
 4. Comorbidities at screening - Our hypothesis is that participants without the clinical comorbidities described above will benefit more than those without these clinical data.
-

Table1 : Flowchart of the procedure: Fluvoxamine, Metformin, and Placebo

[figure not shown]
	Screening and Baseline Day 1	Day 07 ± 3 days	Day 30 ± 7 days	Day 60 ± 7 days	Days 90, 180, EoT, or early termination ± 7 days
Review of initial eligibility criteria	X ⁽¹⁾				
Informed consent for screening	X				
Pregnancy test	X ⁽²⁾				
Second review of eligibility criteria - Conclusion and FSS scoring	X ⁽³⁾				
Informed consent for participation	X				
Demographic data	X				
Medical history	X				
Comorbidities and risk factors	X				
Concomitant medications	X	X	X	X	X
Physical examination	X				
Vital signs (temperature, heart rate, respiratory rate, oxygen saturation)	X			X	
COVID-19 medical history	X				
Randomization	X				
IP administration*	X	X	X	X	
IP Adherence	X	X	X	X	

Concomitant medications	X	X	X	X	X
Fatigue Severity Scale (FSS)	X		X	X	X
Visual Analog Scale of Fatigue Intensity	X		X	X	X
EQ-5D-5L	X	X	X	X	X
Hospitalization		X	X	X	X
Mortality		X	X	X	X
Adverse events (AE)		X	X	X	X

*Fluvoxamine, metformin, and the corresponding placebo will be administered for 60 days s

Fluxograma da Pesquisa

Braços Fluvoxamina, Metformina e Placebo

1. Tratamento: Fluvoxamina, Metformina e placebo em grupos paralelos pelo período planejado. Posologia das medicações varia conforme a alocação do paciente em um braço do estudo (Para cada braço há o correspondente placebo, na mesma formulação e posologia. Medicações serão interrompidas a qualquer momento se houver evidência de reação adversa, a critério do sujeito da pesquisa ou por recomendação do DSMB (eficácia, futilidade ou segurança do participante).
2. Triagem e Randomização devem ser realizadas na mesma visita. Assegurar que o paciente seja randomizado por ocasião do atendimento.
3. As visitas subsequentes: D₃₀ a D₆₀, D₉₀ serão realizadas através de contato telefônico, telemedicina ou aplicativos de mídias sociais, entretanto com possibilidade de visitas presenciais, caso necessário. Em qualquer momento visitas extras de segurança poderão ser realizadas, inclusive presenciais. A visita D₆₀ é considerada a visita de desfecho para a pesquisa. A visita D₉₀ é considerada visita pós-estudo, para acompanhamento de eventuais complicações tardias/ persistência de sintomas relacionados ao COVID-19 e também para avaliação eventual de reações adversas tardias aos medicamentos da pesquisa. Esta será realizada através de contato telefônico. Não há previsão de visitas presenciais regulares nesta pesquisa, entretanto recomendamos que a visita D₆₀ seja preferencialmente realizada presencialmente.
4. Visitas adicionais poderão ser realizadas seja por sugestão da equipe de pesquisa seja por solicitação do participante. |

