2.1 Objectives/Primary Outcome

The primary objective is to compare the use of Fluvoxamine and Metformin with placebo for the mean score on the Fatigue Severity Scale (FSS) on day 60 after randomization by at least 1 point.

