12.3 Sample Size Calculation I

The sample size of 500 participants per arm and its operational characteristics were confirmed using closed-form, analytical, and numerical methods. The operational characteristics for the head-to-head comparison of the treatment arm versus the placebo arm in reducing the mean fatigue score measured by the Fatigue Severity Scale (1 to 9) on day 60 are shown in Table 2. For each pairwise comparison against the placebo arm, the Type I error rate (alpha) was set at 0.025 (one-sided) using a Bayesian normal-normal model. For the planning of our study, we assumed a plausible standard deviation value of 1.7, which was estimated from a recent study that evaluated the psychometric properties of the fatigue severity scale in participants recovering from COVID-19.¹

Table 2 : Simulated operational characteristics of our study for varying sample sizes

Dropout rate	Reduction in FSS score	Sample (n = 252)	Sample (n = 500)	Sample (n = 752)	Sample (n = 1000)
0.0	0.00	2.5%	2.5%	2.5%	2.5%
	0.15	13.2%	22.6%	32.3%	41.5%
	0.30	41.8%	71.2%	87.8%	95.2%

Dropout rate	Reduction in FSS score	Sample (n = 252)	Sample (n = 500)	Sample (n = 752)	Sample (n = 1000)
	0.45	76.8%	97.1%	99.7%	100.0%
2.5	0.00	2.5%	2.5%	2.5%	2.5%
	0.15	12.9%	22.0%	31.5%	40.5%
	0.30	40.6%	69.7%	86.8%	94.7%
	0.45	75.4%	96.6%	99.7%	100.0%
5.0	0.00	2.5%	2.5%	2.5%	2.5%
	0.15	12.6%	21.6%	30.8%	39.6%
	0.30	39.5%	68.5%	85.9%	94.1%
	0.45	73.9%	96.3%	99.6%	100.0%
10.0	0.00	2.5%	2.5%	2.5%	2.5%
	0.15	12.2%	20.6%	29.4%	37.8%
	0.30	37.7%	66.1%	84.0%	92.9%
	0.45	71.5%	95.4%	99.4%	99.9%

Thus, the clinical trial will recruit 1,500 participants, divided into three groups of 500 participants each. With the proposed sample size of 500 participants in each group, the study will have adequate statistical power to detect a clinically significant treatment effect. A difference of 0.45 has been suggested as the minimum clinically important difference (MID) on the fatigue severity scale in population groups of participants with multiple sclerosis and chronic fatigue.² Even with a 10% dropout rate, our estimated power to detect a difference of 0.45 is above 90%.

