12.11 Summary table of analyses from the website

Result	Hypothesis	Outcome Measure	Statistical analysis method
Primary Mean score measured by the fatigue severity scale on day 60 after randomization	Drug treatment will be better than placebo	Fatigue Severity Scale	Bayesian Normal-Normal analysis
Secondary Mean score measured by the fatigue severity scale on day 30 after randomization	Drug treatment will be better than placebo	Fatigue Severity Scale	Bayesian Normal-Normal Analysis
Mean score measured by the fatigue severity scale on day 90 after randomization	Drug treatment will be better than placebo	Fatigue Severity Scale	Bayesian Normal-Normal Analysis
Health-related quality of life on day 60 after randomization	Drug treatment will be better than placebo		Bayesian Normal-Normal Analysis
All-cause mortality by day 60 after randomization	Treatment will prevent overall mortality	Measuring deaths in the groups	Logistic regression
Time to all-cause mortality up to day 60 after randomization	The treatment will prevent overall mortality	Interval in days between randomization and mortality	Cox regression
Unexpected hospitalization from any cause by day 60 after randomization	The treatment will prevent hospitalization	Measurement of deaths in the groups	Logistic regression
Unexpected hospitalization for any cause up to day 60 after randomization	The treatment will prevent hospitalization	Interval in days between randomization and mortality	Cox regression
Safety of the IP	The drugs are safe in participants with long COVID	Measurement of adverse events in treatment groups	Descriptive analysis
3) Subgroup analysis: i) Age (young vs. elderly) (ii) Sex (male vs. female) female)	Older adults are at higher risk of complications Men are at higher risk	Risk assessment	Regression methods with appropriate interaction terms.

iv) Vaccination status	Unvaccinated individuals are at higher risk		
v) Obesity	Obesity carries a higher risk		
vi) Diabetes	Diabetes carries a higher risk		
vii) Hypertension			
viii) Cardiovascular disease	People with high blood pressure are at higher risk		
ix) Chronic lung disease	Lung disease carries a higher risk		
4) Sensitivity analysis	The results remain robust	Primary and key secondary outcomes (fatigue score at day 30 and day 60)	

IMPORTANT NOTES:
 
 In all analyses, results will be expressed as estimated effects with corresponding 95% uncertainty estimates 			

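### The protocol's two formal primary-outcome statements conflict with each other and with the day-60 mean-score analysis for which the trial is powered

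*Protocol*

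**What the plan says.** The current text describes the primary outcome in three ways.

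- **Overview, primary and secondary outcomes:** "The primary outcome is a reduction in the FSS score of at least one standard deviation 60 days after randomization". The SD is not identified (baseline, change or pooled), and neither is the level (patient or group).
- **Section 2.1, headed as the primary objective and outcome:** active drugs are compared with placebo "for the mean score on the Fatigue Severity Scale (FSS) on day 60 after randomization by at least 1 point".
- **Mean score, no threshold:** the Overview objective compares the arms "for the mean Fatigue Severity Scale (FSS) score at 60 days after randomization". The Overview analysis paragraph begins "To analyze the primary outcome of the mean fatigue score at day 60 measured by the Fatigue Severity Scale" and names a Bayesian normal-normal model. The Section 12.11 table lists "Mean score measured by the fatigue severity scale on day 60 after randomization", analysed by the same model, with the hypothesis only that drug beats placebo.

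Section 12.3 gives the planning effect: "A difference of 0.45 has been suggested as the minimum clinically important difference (MID) on the fatigue severity scale". It uses SD 1.7, one-sided alpha 0.025 and 500 per arm. Table 2 shows power of 97.1% without dropout and 95.4% with 10% dropout.

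Section 12.5, the body-text counterpart of the Overview analysis paragraph, places the primary analysis at day 90. Both it and the Overview assign binary outcomes to logistic regression.

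**The concern.** A reader looks for the primary outcome under the headings that name it, and there finds two thresholds that differ from each other. Neither appears in the analysis text, the summary table or the sample size. Nothing in the protocol ties the one-SD or the one-point requirement to a model, or reconciles either with 0.45.

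The readings can give different answers from the same data. A modest but clear mean benefit would succeed on the mean-score test and fail a one-point minimum. A one-SD patient-level outcome would be a different variable, under a different model, with power the protocol never states. The interim efficacy and futility rules also need one defined variable at one time point.

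**Working it through.** **Inputs.** SD 1.7, difference 0.45, one-sided alpha 0.025, 500 per arm and 10% dropout (450 evaluable) come from Section 12.3. The three interims at 25%, 50% and 75%, hence four looks, come from Section 12.1.2. The stopping boundary is not printed in the protocol, so the constant boundary below is an assumption.

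**1. Reproducing the plan's power.** SE = 1.7 × √(2/n).

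- n = 500: SE = 0.1075; fixed-design power = Φ(0.45/0.1075 − 1.96) = 98.7%.
- n = 450: SE = 0.1133; fixed-design power = Φ(0.45/0.1133 − 1.96) = 97.8%.
- Four equally spaced looks with a constant boundary of 2.361 (simulated): 97.3% and 95.7%, against 97.1% and 95.4% in Table 2.

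Table 2 therefore reproduces as power for a difference in means of 0.45. That calculation is not in error.

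**2. The thresholds side by side.** One SD, if the planning SD is meant, is 1.7 points, and 1.7/0.45 = 3.8 times the planning difference. One point is 1/0.45 = 2.2 times it.

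**3. One point read as a required observed difference, true effect 0.45.**

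- n = 500: (1 − 0.45)/0.1075 = 5.1; upper tail 1.6 × 10⁻⁷.
- n = 450: (1 − 0.45)/0.1133 = 4.85; upper tail 6 × 10⁻⁷.

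**4. Where the two mean criteria disagree, 450 per arm.** The smallest difference that passes the mean test is 1.96 × 0.1133 = 0.22 (fixed design) or 2.361 × 0.1133 = 0.27 (constant boundary, final analysis). Results from there up to 1.0 pass the mean test and fail the one-point minimum. That interval contains 0.45, the difference the protocol cites as minimally important.

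**5. The one-SD statement read as a patient-level event.** The outcome becomes binary and falls under logistic regression, not the normal-normal model. Its power needs the SD of change and the placebo improvement, which the protocol does not give. For illustration only, take a 1.7-point cut, a 0.45 shift, 450 per arm, normal changes and a fixed design:

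| SD of change (assumed) | Mean placebo fall (assumed) | Power |
|---|---|---|
| 1.7 | 0 to 1 point | 78% to 88% |
| 1.2 to 2.4 | 0 to 1 point | 55% to 99% |

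The width of that range shows that Table 2 does not carry over. It does not show what the power would be.

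**6. Effect on the error rate.** An observed difference of 1 point gives z = 1/0.1133 = 8.8, so every result that meets the one-point minimum also passes the mean test. Choosing between those two criteria cannot raise the type I error. A free choice between the mean test and a separate responder test, each at 0.025, could raise it, but to no more than 0.025 + 0.025 = 0.05.

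**The case against.** The strongest reply is that the intended analysis is plain. The objective, sample size, Overview analysis and summary table all use the mean FSS score at day 60. Section 2.1 also names the mean at day 60, so only the Overview outcome entry can be read as a different variable. The Overview leaves the decision rules to the SAP, and Section 3.1 says the thresholds are calibrated by simulation. Most of this stands, and it limits the point in four ways.

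- A reader might infer that the trial has three rival outcome definitions and no success criterion at all. The text does not support that. The 0.45 figure is a planning difference, fully compatible with a mean-score outcome, and the success threshold may well be in the SAP, which is not shown.
- A reader might infer that control of the 0.025 error rate is lost. That would require the choice between the mean and a responder test to stay open until unblinding, which the protocol does not say.
- A reader might take the one-SD entry as certainly a responder outcome and treat its lower power as a finding. The entry does not state the level, and the power figures depend on outside assumptions.
- Section 2.1 is loosely worded and may express a hoped-for effect rather than a decision rule. The calculation in step 3 is conditional on the stricter reading.

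What remains is that the entries carrying the primary-outcome label contradict the analysis. A SAP that adopts one reading would still conflict with the protocol's other statements.

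**Conclusion.** The protocol contradicts itself on its primary outcome and should be amended. The mean difference in FSS at day 60 is the dominant reading and the only one with stated power. The one-SD entry in the Overview and the one-point clause in Section 2.1 agree neither with it nor with each other, and Section 12.5 adds a conflict over the time point.

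The size depends on the reading. As a required observed difference, one point would almost never be met by a true 0.45 effect (under 1 in a million), and observed results from about 0.22–0.27 to 1.0 would be judged in opposite ways. These figures rest on the protocol's SD of 1.7 and 450 to 500 per arm; the 0.27 limit also rests on an assumed constant boundary. As a patient-level event, the one-SD outcome has no stated power and would not be analysed by the model named for the primary outcome. The existing power calculation for the mean is sound.

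**What to change.** State one primary outcome in every place: the difference in mean FSS score versus placebo at day 60, with success judged by the calibrated posterior threshold. Specifically:

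- **Section 2.1:** delete the closing clause that sets a one-point minimum.
- **Overview, primary outcome:** replace the one-SD statement. If it is wanted, keep it as a secondary responder analysis, stated as patient-level, with the cut fixed in points.
- **Section 12.5:** change day 90 to day 60 for the primary analysis.
- **Section 2.2:** settle in the same amendment the entry that lists the day-60 mean as a secondary objective, where the Overview has day 90.

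On this course the cost is a wording amendment, with no change to sample size, visits or data collection. If the sponsor instead intends the one-SD or one-point criterion as primary, that is its decision, but the analysis model and the power statement must then be redone for it, which is more than a wording change.
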